## LIST OF ABBREVIATIONS AND RELEVANT DEFINITIONS

3D	Three Dimensional
AE	Adverse Event
CABG	Coronary Artery Bypass Grafting
CV	Curriculum Vitae
IC	Informed Consent
METC	Medical research ethics committee (MREC); in Dutch: medisch-ethische toetsingscommissie (METC)
RCT	Randomized Control Trial
(S)AE	(Serious) Adverse Event
VR	Virtual Reality
WMO	Medical Research Involving Human Subjects Act; in Dutch: Wet Medisch-wetenschappelijk Onderzoek met Mensen

## SUMMARY

**Rationale:** Post-operative pain and anxiety are common problems in cardiac surgery. These two components can lead to many adverse outcomes in patients, resulting in a longer recovery time and a lower overall well-being. Common treatment of these problems is by use of analgesics such as opioids, NSAIDS and paracetamol. However, analgesics come with side effects which affect the quality of life. Therefore there is a need for alternative pain and anxiety management.

Virtual Reality (VR) modalities are currently emerging as non-pharmacological tools for post-operative pain and anxiety management. Earlier studies in other surgical fields showed the potential positive effects of VR modalities on postoperative pain and anxiety. However, such a study is never performed in the field of cardiac surgery. Therefore we decided to perform a randomized control trial (RCT) in which we assess the feasibility of VR in postoperative pain and anxiety management in the field of cardiac surgery.

**Objective:** The objective of this study is to investigate the effect of VR on post-operative pain and anxiety management in cardiac surgery patients undergoing a coronary artery bypass grafting (CABG) procedure.

**Study design:** This study is a single-center randomized control trial.

**Study population:** Patients who have undergone a CABG procedure (n=100).

**Intervention:** The intervention group (n=50) will use the VR distraction therapy device at day 1, 2 and 3 after surgery on the general ward. The control group (n=50) will be treated with conventional post-operative pain and anxiety management.

**Main study parameters/endpoints:** The main study parameters at day 1, 2 and 3 after surgery. These are the Numeric Rating Scale (NRS) to assess the effect of pain on mobility, the Quality of Recovery-15 questionnaire, the State-Trait Anxiety Inventory-6 questionnaire and assessment of analgesic use. At follow-up, participants will be called to gather one-time QoR-15 and STAI-6 questionnaire data 6 weeks after the surgery.

**Nature and extent of the burden and risks associated with participation, benefit and group relatedness:** This is a study with use of a digital VR distraction therapy device. This device is known to have potential adverse effects of nausea and dizziness. However, the

used software is optimized to minimize these adverse effects. And the potential benefits of reducing pain and anxiety in the post-surgical phase outweigh these potential adverse effects.

## 1. INTRODUCTION AND RATIONALE

Post-operative pain and anxiety are common problems in all surgical fields.[1] These pain and anxiety are due to the surgical tissue damage and the unpleasant psychological experience of undergoing a surgical procedure.[2] Those two components can lead to many adverse outcomes in patients, resulting in a longer recovery time and a lower overall well-being.[3] Pain and anxiety levels after cardiac surgery are often more severe than average due to the relative more invasive surgical procedures. The incidence of chronic pain and/or anxiety after cardiac surgery is 21-55%.[4] The occurring pain syndromes know a wide variety (visceral, musculoskeletal or neurogenic) and are commonly treated by use of analgesics such as opioids, NSAIDS and paracetamol. However, due to the many side effects of these analgesics which affect the quality of life [5] there is a need for alternative pain and anxiety management.

Virtually Reality (VR) modalities are currently emerging as non-pharmacological tools for post-operative pain and anxiety management. The effective potential of these modalities are due to their possibilities for distraction from reality, resulting in distraction therapy. Virtual reality environments are taught to divert the patients attention away from the nociceptive input, resulting in less attention for pain perception and therefore more comfort in the clinical recovery path.

A recently published systematic review and meta-analysis [6] showed that the effects in general are still not clear as several studies yielded both positive and non-significant results for VR distraction therapy devices. The preliminary conclusion on this is that the application of VR distraction therapy can relief post-operative pain and anxiety, however this could not be stated firmly yet because of the heterogeneity in most studies due to different types of surgery and various timing of VR usage.

Also, there are no studies performed yet in the field of cardiac surgery concerning post-operative pain and anxiety management using VR distraction therapy. Therefore we decided to perform a randomized control trial (RCT) in which we assess the feasibility of VR in postoperative pain and anxiety management in the field of cardiac surgery. Also we will assess if there are predictive factors to select specific patients who can mostly benefit from this innovative intervention. The used VR distraction therapy device in this study will be the Healthy Mind VR device. This is a CE-mark Class I device.[7]

## 2. OBJECTIVES

Primary Objective: To investigate the effect of VR distraction therapy with breathing exercises in post-operative pain and anxiety management in cardiac surgery patients undergoing coronary artery bypass grafting (CABG) procedure.

### 3. STUDY DESIGN

This study is a single-center randomized control trial.

The study will consist of 100 participants who have undergone an uncomplicated surgical CABG procedure. The intervention group includes 50 patients using a VR distraction therapy device with 3D interactive nature environments in the post-operative stage for pain and anxiety management and breathing exercises. The VR distraction therapy device consists of a head-mounted display and a configuration tablet. The control group includes 50 patients who will be treated with conventional post-operative pain and anxiety management.

The intervention group will test-use the VR distraction therapy device on the day of clinical admission prior to surgery and use it therapeutic at day 1, 2 and 3 after surgery on the general ward. Daily usage of this tool consists of two sessions each day (morning and afternoon) with a duration of 20 minutes per session. The specific virtual environment for each session will be selected freely by the participants.

Outcomes will be measured daily, at the end of each session. Outcomes will be measured by using the Numeric Rating Scale (NRS) to assess the effect of pain on mobility (in retrospect), Quality of Recovery-15 (QoR-15) questionnaire, State-Trait Anxiety Inventory-6 (STAI-6) questionnaire and assessment of analgesic use.

At follow-up, participants will be called to gather one-time QoR-15 and STAI-6 questionnaire data 6 weeks after the surgery.

P	100 participants who have undergone an uncomplicated surgical CABG procedure
I	VR distraction therapy device with 3D interactive nature environments in the post-operative stage for pain and anxiety management. 50 participants will use the VR distraction therapy device at day 1, 2 and 3 after surgery on the general ward. Daily usage of this tool consists of two sessions each day (morning and afternoon) with a duration of 20 minutes per session. 6 week after surgery data on pain and anxiety at follow-up will be gathered by phone call using two questionnaires.
C	Conventional post-operative pain and anxiety management in 50 participants
O	

• Numeric Rating Scale (NRS) to assess the effect of pain on mobility

• Quality of Recovery-15 (QoR-15) questionnaire

• State-Trait Anxiety Inventory-6 (STAI-6) questionnaire

• Assessment of analgesic use

#### 4. STUDY POPULATION

##### 4.1 Population (base)

The study population consists of patients who are  $\geq 18$  years of age and have undergone a surgical CABG procedure.

##### 4.2 Inclusion criteria

In order to be eligible to participate in this study, a subject must meet all of the following criteria:

- Age  $\geq 18$  years or older with written informed consent
- Patients undergoing surgical CABG

##### 4.3 Exclusion criteria

A potential subject who meets any of the following criteria will be excluded from participation in this study:

- Major comorbidities besides coronary artery disease
- Complicated surgical procedure
- Hearing and/or visual impairments
- Psychiatric impairments
- Complaints of vomiting and nausea
- History of epilepsy
- Claustrophobia
- Facial wounds and skin defects at site of application
- Patients placed in clinical isolation
- Readmission to the intensive care unit

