### **7.2 Randomisation, blinding and treatment allocation**

For randomisation, we use a simple random allocation approach. This randomization sequence will be prepared in SPSS 26.0 (SPSS Inc, Chicago, IL) for Windows. This randomization will be performed postoperatively by the research team, in case of an uncomplicated procedure, directly after the patient returns to the clinical ward after surgery. Blinding however, is not possible in this study as usage of the medical device is clear.

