### **7.3 Study procedures**

The study will consist of 100 participants who have undergone an uncomplicated surgical CABG procedure.

The intervention group includes 50 patients using a VR distraction therapy device with 3D interactive nature environments in the post-operative stage for pain and anxiety management. The control group includes 50 patients who will be treated with conventional post-operative pain and anxiety management.

The intervention group will test-use the VR distraction therapy device on the day of clinical admission prior to surgery and use it therapeutic at day 1, 2 and 3 after surgery on the general ward.

Daily usage of the VR distraction therapy device consists of two sessions each day (morning and afternoon) with a duration of 20 minutes per session. The specific virtual environment for each session will be selected freely by the participants.

Outcomes will be measured daily, at the end of each session, which is done 1) after the doctor's ward visit in the morning and 2) after the shift change of the nurse team.

Outcomes will be measured at the same aforementioned moments in the control group.

Outcomes will be measured by using the Numeric Rating Scale (NRS) to assess the effect of pain on mobility, Quality of Recovery-15 questionnaire, State-Trait Anxiety Inventory-6 questionnaire and assessment of analgesic use.

At follow-up, participants will be called to gather one-time QoR-15 and STAI-6 questionnaire data 6 weeks after the surgery.

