### **7.5 Replacement of individual subjects after withdrawal**

Upon withdrawal of a subject, the data collected will not be used for the study and will be deleted.

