#### **7.6 Follow-up of subjects withdrawn from treatment**

Not applicable.

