#### 8.2.2 Serious adverse events (SAEs)

A serious adverse event is any untoward medical occurrence or effect caused by the study that

- results in death;
- is life threatening (at the time of the event);
- requires hospitalisation or prolongation of existing inpatients' hospitalisation;
- results in persistent or significant disability or incapacity;
- is a congenital anomaly or birth defect; or
- any other important medical event that did not result in any of the outcomes listed above due to medical or surgical intervention but could have been based upon appropriate judgement by the investigator.

An elective hospital admission will not be considered as a serious adverse event.

The direct investigator will report all SAEs which are caused by the study to the principal investigator without undue delay after obtaining knowledge of the events.

The investigator will report these SAEs through the web portal *ToetsingOnline* to the accredited METC that approved the protocol, within 7 days of first knowledge for

SAEs that result in death or are life threatening followed by a period of maximum of 8 days to complete the initial preliminary report. All other SAEs will be reported within a period of maximum 15 days after the investigator has first knowledge of the serious adverse events.

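### ICU readmission is an exclusion criterion with no time limit, yet randomisation takes place directly on return to the ward, so the criterion is either nearly empty or is applied to patients already randomised

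*Combined protocol and SAP*

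**What the plan says.** Section 4.3 opens its list with "A potential subject who meets any of the following criteria will be excluded from participation in this study". One of the listed items is "Readmission to the intensive care unit". No date or window is attached to it.

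Section 7.2 has the research team randomise after surgery, "in case of an uncomplicated procedure, directly after the patient returns to the clinical ward after surgery". Section 7.3 has the intervention group "use it therapeutic at day 1, 2 and 3 after surgery on the general ward". The main outcomes are collected on the same days in both arms, and QoR-15 and STAI-6 again by telephone at 6 weeks. Section 7.2 also states that blinding is not possible.

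On patients who leave the study, 7.5 says: "Upon withdrawal of a subject, the data collected will not be used for the study and will be deleted". Section 7.6, headed "Follow-up of subjects withdrawn from treatment", is marked as not applicable. Section 9.1 specifies rank-sum tests for each day and on cumulative means. It names no analysis population and gives no rule for missing data.

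**The concern.** An eligibility criterion should depend only on what is known when the patient is randomised. Return to intensive care normally happens later, and it is itself a sign of a poor recovery. If the study team applies the criterion when the event occurs, the arms are compared only among patients who did well enough to stay on the ward. That conditions the comparison on a post-randomisation outcome, and one of the main outcomes, QoR-15, is a measure of recovery.

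The criterion covers both arms. Bias arises if readmission, or the decision to remove the patient, differs between them. The second is possible because the staff applying the criterion know the allocation. Even balanced removal departs from the comparison of patients as randomised.

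There is also a loss of information. Sections 8.2.1 and 8.2.2 cover only events regarded as caused by the study. An ICU readmission judged unrelated, in a patient then treated as ineligible, would not be counted by arm anywhere.

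**Working it through.** **1. Can the criterion be met before randomisation?** The order of events in the protocol is: consent signed at admission (10.2), surgery, return to the ward, randomisation directly afterwards if the procedure was uncomplicated (7.2), then days 1 to 3 on the ward (7.3). A readmission can occur only after a first discharge from intensive care. The only window before randomisation is the short gap between arrival on the ward and the act of randomising. The protocol describes no step that would lengthen it.

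**2. What happens if it is met afterwards?** No section answers this directly. The relevant texts are:

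- 6.3 and 12.1e: participants who develop VR-related symptoms are excluded from taking further part.
- 7.7: patients who experience such symptoms are described as not included in the study.
- 12.1g: all included subjects are described as stable and on the general ward, which a readmitted patient is not.
- 7.4: the investigator may withdraw a subject for urgent medical reasons.
- 7.5 and 7.6: data of withdrawn subjects are deleted, and there is no follow-up.
- 9.1: no analysis set retains such patients.

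The protocol therefore uses eligibility wording for later events, and nothing in it keeps a readmitted patient in the analysis.

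**3. How many patients?** The documents give no readmission rate, so the rate *r* is an assumption. The expected number among 100 is 100*r*, and the chance of at least one is 1 − (1 − *r*)^100.

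| Assumed *r* | Expected of 100 | Chance of at least one |
|---|---|---|
| 1% | 1 | 63% |
| 2% | 2 | 87% |
| 5% | 5 | 99% |
| 10% | 10 | >99.9% |

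These figures show how likely the question is to arise. They do not measure bias.

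**4. Is power the problem?** First, the plan's own figure. From the Table 1 proportions (X, Y), P(X<Y) = 0.2395 and P(X=Y) = 0.1439. So p = 0.2395 + 0.5 × 0.1439 = 0.311, as in Table 1. With n per arm and mean category proportions z across the two arms:

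- Null variance with tie correction: v0 = (2n+1)/(12n²) × (1 − Σz³). At n = 50, Σz³ = 0.0356, so √v0 = 0.0570.
- Variance under the Table 1 alternative: √v1 = 0.0523.
- Power = Φ[(|p − 0.5| − 1.96√v0)/√v1] = Φ[(0.1885 − 0.1117)/0.0523] = Φ(1.47) = 92.9%.

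The protocol states 92.7%, so its figure reproduces closely. A simulation of 5,000 trials gave 93.0%.

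Next, balanced loss unrelated to outcome:

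| Assumed loss | Per arm | Power |
|---|---|---|
| 2% | 49 | 92.4% |
| 5% | 47 to 48 | 91.3% to 91.9% |
| 10% | 45 | 90.0% |

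Power is barely affected. The issue is which patients are lost.

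**5. Can the bias be sized?** No. That would need readmission rates by arm and the outcomes of readmitted patients, and the documents give neither.

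**The case against.** The strongest reply is textual. Section 4.3 speaks of a potential subject, and a randomised patient is no longer one. Where the protocol means removal after the start, as in 6.3 and 12.1e, it refers to participants being excluded from further participation. On that reading 4.3 is a screen before enrolment, and no section says that a readmitted randomised patient is dropped. This is a fair reading, and it rules out saying that the protocol requires such removal. It does not clear the problem, because it leaves the criterion with almost nothing to act on while 6.3, 7.7 and 12.1e show eligibility language being used for later events. The text needs clarifying on either reading.

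A second reply is that a window before randomisation does exist. It does, but it is narrow. It is a reason to put a time limit on the criterion and not to delete it, since deletion would also admit patients readmitted before randomisation.

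A third reply is that the harm comes from 7.5, 7.6 and 9.1. Much of it does, and correcting those sections would remove most of it. A criterion that can label a later event as ineligibility would still remain.

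Two stronger readings are tempting and are not supported:

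- A reader might infer that a planned safety comparison is spoiled. No between-arm safety comparison is planned, and serious events caused by the study must still be reported to the ethics committee. What is lost is by-arm counts and denominators.
- A reader might put a figure on the bias from Table 1. The means there are 4.77 and 3.548, a difference of 1.222. Removing two patients with NRS 8 from the first arm alone gives (50 × 4.77 − 16)/48 = 4.635, a shift of 0.135, or 11% of the difference. The arithmetic is right, but nothing in the documents links ICU readmission to a score of 8 or puts all the losses in one arm. Some of those readings would also be missing whatever 4.3 says.

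**Conclusion.** The point holds as an ambiguity with a real consequence. Sections 4.3 and 7.2 together leave the ICU readmission criterion either nearly empty or applied after randomisation, and no other section keeps a readmitted patient in the analysis. If it is applied after randomisation, the comparison of QoR-15, NRS and STAI-6 is conditioned on a later outcome in an open-label trial.

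The bias cannot be sized or signed from the documents. The cost in power is small: about 92.4% to 90.0% under an assumed 2% to 10% loss that is balanced and unrelated to outcome. The conclusion rests on randomisation taking place promptly on the ward, as 7.2 describes, and on a readmitted patient being handled as a withdrawal. The second is a plausible reading of the protocol but is not stated in it.

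**What to change.** In 4.3, state that all criteria, including ICU readmission and clinical isolation, are judged on status up to the moment of randomisation.

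In 9.1, with matching wording in 7.5 and 7.6, state that a patient readmitted to intensive care after randomisation stays in the analysis set in the arm assigned. Data already collected are kept, the 6-week call is attempted, and readmissions are recorded in both arms and reported by arm. Whether VR sessions take place around a readmission is left to the investigators.

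The cost is a wording amendment and one event field on the case report form. Some day 1 to 3 readings will be missing for these patients, so 9.1 also needs a stated rule for missing data.

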##### 4.4 Sample size calculation

In total, 100 subjects will be included in this study. 50 subjects in the patient group that will receive VR therapy and 50 subjects in the patient group that will not receive VR therapy. Since literature is limited about our primary outcomes in the field of cardiac surgery, a retrospective pilot was done in our clinical pool of CABG patients for the assessment of one of our primary outcomes (NRS-score) upon which we based our sample size calculation. See below for details.

A retrospective assessment for NRS-score is performed in 35 patients who have undergone an uncomplicated CABG procedure in our department the past year (2020). Since the data was non-normally distributed, a two-sided Wilcoxon (Mann-Whitney) Rank-Sum test was performed in nQuery Advisor version 8.5.1 [8] on Windows with  $P(X < Y) = 0.5$  and a test significance level of 0.05. Since this statistical test allows only a maximum

of 8 categories and none of the pilot patients scored 0, 9 or 10 for the NRS-score, only NRS-scores 1 - 8 were used as categories in this test. This resulted in a power of 92,7% for a sample size of 100 subjects (50 per group) (**Table 1**).

MTT2-1 / Wilcoxon (Mann-Whitney) Rank-Sum Test that $P(X < Y) = 0.5$		
	1	2
Test Significance Level, $\alpha$	0,050	0,050
1 or 2 Sided Test?	2	2
Number of Categories, k	8	8
Side Table Name	MTT2S-1	MTT2S-2
$p_1 = P(X < Y)$	0,311	
Power (%)	92,7	92,7
▶ Sample Size per Group, n	50	50

  

Category	Proportion in Group 1 (X)	Proportion in Group 2 (Y)
1	0,059	0,050
▶ 2	0,059	0,302
3	0,088	0,180
4	0,328	0,250
5	0,119	0,050
6	0,147	0,090
7	0,060	0,060
8	0,140	0,018
$\sum \pi_i$	1,000	1,000
$p_1 = P(X < Y)$	0,311	

**Table 1.** Sample size calculation using a two-sided Wilcoxon (Mann-Whitney) Rank-Sum test in nQuery Advisor version 8.5.1 on Windows with  $P(X < Y) = 0.5$ .

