### 6.3 Summary of known and potential risks and benefits

#### Potential risks:

Some patients may present a non-adherence to the VR relaxation technique, resulting in discomfort and/or nausea and dizziness. The limitations of VR can be related to lacking physical adaptation which can potentially result in cyber-sickness.

The brain uses three sources of data to inform the body about its position and movements: the inner ear, muscles, and eyes. Once the head mounted display is on your head, the eyes indicate that you are in a different environment, but the inner ear and muscles say that this is not the case: this inconsistency of sensory information usually translates into temporary symptoms such eye fatigue, disorientation (dizziness, imbalance) and nausea. However, the Healthy Mind software was created specifically for patients with reduced mobility (lying or sitting) and optimized to minimize adverse effects such as nausea. For example, the user is not in constant movement in the virtual environment. Users remain static and are being teleported to new areas of the environment. This way, the gap between the inner ear and the virtual world is minimized. Furthermore, participants in this study will be excluded from further participation as soon as the above mentioned symptoms are noticed.

Potential benefits:

The VR technique of Healthy Mind uses the brain's cognitive and affective capacities to modulate pain pathways through combined visual and auditory stimulations, attention diversion and relaxation. The software on this device puts patients in immersive experiences in VR to distract them from reality. The software also integrates breathing exercises which are essential in the postoperative setting in cardiac surgery for lung recovery.

Altogether, the potential benefits of these elements would be pain reduction, anxiety reduction, improved lung recovery and faster general post-operative recovery.

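### The 92.7% power in section 4.4 holds only if all 100 patients are analysed; section 7.5 deletes withdrawn patients' data, which costs a little power and, more seriously, comparability of the arms

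*Combined protocol and SAP*

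**What the plan says.** Section 4.4 fixes the number enrolled: "In total, 100 subjects will be included in this study", split 50 and 50. It then gives the power: "This resulted in a power of 92,7% for a sample size of 100 subjects (50 per group". The method is stated: "a two-sided Wilcoxon (Mann-Whitney) Rank-Sum test was performed in nQuery Advisor version 8.5.1", with "a test significance level of 0.05". The inputs are the eight category proportions per group in Table 1. No dropout rate, inflation, evaluable-patient target or minimum acceptable power appears.

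Section 7.5 is headed as dealing with replacement, but its only content is: "Upon withdrawal of a subject, the data collected will not be used for the study and will be deleted". It neither provides for replacement nor rules it out. Section 7.6, on follow-up after withdrawal from treatment, gives no procedure.

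Section 6.3 describes eye fatigue, disorientation and nausea as possible effects of the headset and adds: "participants in this study will be excluded from further participation as soon as the above mentioned symptoms are noticed". Section 12.1 e repeats this for nausea and dizziness. Section 7.2 places randomisation at the return to the ward, before any therapeutic session.

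Section 9.1 compares the groups on each of days 1, 2 and 3 and on means across days. It defines no analysis population and no handling of missing data.

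**The concern.** Two parts of the plan do not fit together. The power calculation treats every enrolled patient as analysed, while the withdrawal rule takes patients out of the data set altogether. Any unreplaced withdrawal therefore lowers power below the stated figure, and a reader of 4.4 is not told so.

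More is at stake in who is removed than in how many. Device-induced symptoms during a therapeutic session can arise only in the VR arm, and only after randomisation. If those patients' data are deleted, the VR arm loses those who tolerated the device worst, with no matching removal among controls. If they would have reported worse pain, recovery or anxiety, the remaining comparison is tilted towards VR. Enrolling more patients would not cure that.

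**Working it through.** **Inputs.** All are from section 4.4 and Table 1: two-sided rank-sum test, alpha 0.05, 50 per group, NRS categories 1 to 8.
- Group 1 (X): 0.059, 0.059, 0.088, 0.328, 0.119, 0.147, 0.060, 0.140.
- Group 2 (Y): 0.050, 0.302, 0.180, 0.250, 0.050, 0.090, 0.060, 0.018.

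Both sum to 1.000. The mean scores are 4.77 and 3.55, so I take X as control and Y as VR; the table does not label them.

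**Effect size.** θ = P(X<Y) + ½P(X=Y) = 0.2395 + ½ × 0.1439 = 0.3115, which agrees with the 0.311 in Table 1.

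**Reproducing the plan's figure.** A normal approximation is power = Φ[(|θ − 0.5| − 1.96 × SD0) / SD1].
- SD0² = (1 − Σp̄³) × N / (12 n₁n₂), where p̄ are the pooled proportions and Σp̄³ = 0.0356. At 50/50: 0.9644 × 100 / 30,000 = 0.003215, so SD0 = 0.0567.
- SD1² = [(n₂−1)v_X + (n₁−1)v_Y + v_h] / (n₁n₂). Here v_X = 0.0695 and v_Y = 0.0664 are the variances of the X and Y placements in the other group, and v_h = 0.1785 is the variance of the single-pair score (1, ½ or 0). At 50/50: (49 × 0.0695 + 49 × 0.0664 + 0.1785) / 2,500 = 0.00274, so SD1 = 0.0523.
- Power = Φ[(0.1885 − 1.96 × 0.0567) / 0.0523] = Φ(1.48) = 93.1%.

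Simulating the tie-corrected test from the same proportions (200,000 replicates) gives 92.7%. The plan's figure is reproduced. The cruder Noether formula gives Φ(√(12 × ¼ × 100) × 0.189 − 1.96) = Φ(1.31) = 90.6%. It ignores the smaller variance under the alternative and does not show the stated figure to be wrong.

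**Power when fewer are analysed.** The loss rates are assumptions; the documents give none.

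| Assumed loss | Analysed control/VR | Simulation | Approximation |
|---|---|---|---|
| None | 50/50 | 92.7% | 93.1% |
| 10% of VR only | 50/45 | 91.4% | 91.7% |
| 20% of VR only | 50/40 | 89.4% | 89.9% |
| 30% of VR only | 50/35 | 87.2% | 87.5% |
| 10% of both | 45/45 | 89.8% | 90.2% |
| 20% of both | 40/40 | 86.1% | 86.4% |
| 30% of both | 35/35 | 81.0% | 81.3% |

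In the approximation, power drops below 80% only under about 34 per arm, which is a loss of (50 − 34)/50 = 32%. With the Noether formula the point is about 37 per arm, a loss of 26%.

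**Simple randomisation.** Section 7.2 says "we use a simple random allocation approach", so an exact 50/50 split is not guaranteed. Averaging over the possible splits of 100 costs about 0.3 points (90.3% against 90.6% by Noether), which is negligible.

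**Which patients are deleted.** Section 7.4 describes withdrawal as the patient's choice or an investigator decision for urgent medical reasons. Sections 6.3 and 12.1 e end participation on symptoms without using the word withdrawal. Section 7.6 provides no follow-up, and section 7.7 says that patients with these symptoms are not to be in the study. Together these suggest that symptom exclusions are handled as withdrawals and deleted, but no sentence says so. The size of any bias cannot be computed, because the documents give neither the exclusion rate nor the outcomes of such patients.

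**The case against.** The strongest reply is that nothing was miscalculated: 92.7% is stated for 50 per group and is right for 50 per group. A reader might infer that the design fails to deliver its stated power, or that the trial is underpowered. The documents support neither. The shortfall exists only if loss occurs and is not replaced, no loss rate is given, replacement is unspecified rather than forbidden, and no target power is set that could be missed.

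The documents also point towards limited loss on the powered outcome. NRS is collected on the ward on days 1 to 3, and the six-week call gathers only QoR-15 and STAI-6, so a missed call need not cost NRS data. Patients with nausea or vomiting complaints are excluded at entry (4.3), VR patients try the device before surgery, and randomisation waits for an uncomplicated procedure. Sections 6.3 and 12.1 e call the symptoms potential and say that the software is designed to minimise them. It would go too far to read them as a predicted rate of VR-arm loss.

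A drop of a few points is also small beside the uncertainty in Table 1 itself, since 4.4 gives no source for the second group's distribution.

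All of this stands, and it reduces the power issue to a note. It does not answer the deletion rule. That rule is explicit, it operates after randomisation, and section 9.1 contains nothing to offset it.

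**Conclusion.** The point holds in a limited form. The 92.7% is correct and conditional: it needs 50 analysed per arm, and the plan has no loss allowance or replacement rule. At an assumed 10% to 20% loss, the reduction is about 1 to 3 points if only the VR arm is affected and about 3 to 7 points if both arms are. Power stays near 81% even at 35 per arm. These figures rest on the Table 1 proportions being true and on the assumed loss rates.

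The weightier part is the instruction in 7.5 to discard data from randomised patients. This departs from analysis as randomised whatever the reason for withdrawal. That it would bias the comparison towards VR rests on two further conditions: that symptom exclusions are treated as withdrawals, and that those patients would have scored worse. Both are plausible and neither is stated, so the bias is a risk that the plan leaves open, not a demonstrated result.

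**What to change.** In section 7.5, replace the deletion rule with one that keeps all data collected up to withdrawal and analyses them in the arm to which the patient was randomised, unless the patient withdraws permission for their use. Say that the same data rule covers participants whose participation ends under 6.3 and 12.1 e. This concerns the data only and leaves those clinical rules untouched.

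In section 4.4, add one sentence: 92.7% assumes that all 100 patients are analysed; at an assumed loss of 10% or 20% it would be about 91% or just under 90% if only the VR arm is affected, and about 90% or 86% if both arms are. Label the loss rates as assumptions.

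No increase in sample size is needed. The costs are a slightly less favourable stated power and some incomplete day 1 to 3 records, for which 9.1 will need a stated handling. Keeping data up to withdrawal recovers only part of the information, because later measurements remain missing.
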